4.4.3 Lost to Follow-up

A patient will be considered lost to follow-up if he/she repeatedly fails to return for scheduled visits and is unable to be contacted by the study site.

Sponsor Name: Aclaris Therapeutics Inc. Protocol Number: ATI-450-CAPS-201 Version and Date: 2.0 24 Sep 2020

Page 35 of 71

The following actions must be taken if a patient fails to return to the clinic for a required study visit:

- The site must attempt to contact the patient and reschedule the missed visit as soon as possible, counsel the patient on the importance of maintaining the assigned visit schedule, and ascertain whether or not the patient wishes to and/or should continue in the study.
- Before a patient is deemed lost to follow-up, the investigator (or designee) must make every effort to regain contact with the patient (where possible, two telephone calls and, if necessary, a certified letter to the patient's last known mailing address or local equivalent methods). These contact attempts should be documented in the patient's research record.
- Should the patient continue to be unreachable, he/she will be considered to have withdrawn from the study.

5 DESCRIPTION OF STUDY ASSESSMENTS

Refer to Table 1 for the Schedule of Assessments.

5.1 Demographics and Other Screening Assessments

Screening assessments that are also part of the safety assessments are described in Section 5.3.

5.1.1 Medical History

Relevant medical history and current medical condition, including CAPS disease phenotype and duration as well as date of first diagnosis and previous treatments including any previous biologic or non-biologic therapy for CAPS will be recorded in the eCRF.

At the baseline visit, inclusion/exclusion criteria will be reviewed and updated to ensure the patient remains qualified for the study. Findings that are observed after the patient has signed the Informed Consent Form (ICF) and prior to the first dose of ATI-450 will be recorded as medical history on the eCRF. Any adverse event observed after the patient has signed the ICF that meets the definition of a SAE (See Section 7.1.2), in which case, all applicable safety reporting procedures will be followed by the site.

5.1.2 Demographics

Demographic data, including year of birth/age, sex (at birth), and race will be recorded in the eCRF.

5.1.3 Tuberculosis Test

An interferon-gamma release assay/QuantiFERON TB Gold test for active/latent TB will be performed at screening with analysis conducted by the sponsor's designated central laboratory. Patients with a negative test result will be eligible for the study.

In case of indeterminate results, the test may be repeated once. The patient can be included in the study if the repeat test is negative; however, if the repeat test is positive or indeterminate, the patient will be excluded from the study.

5.1.4 Screening Clinical Laboratory Assessments

Blood samples will be collected for clinical chemistry, coagulation, hematology, hsCRP, SAA, and lipids, follicle-stimulating hormone (FSH), HBsAg, hepatitis B core antibody, hepatitis C antibody, and HIV-1/HIV-2. A serum pregnancy test will be performed on women of childbearing potential. All laboratory analyses will be performed by the sponsor's designated central laboratory.

5.1.5 COVID-19 Monitoring

At Baseline Visit 2, all patients entering the treatment phase of the study must have a nasopharyngeal (preferred) or oropharyngeal swab collected prior to the first dose of ATI-450 to test for the presence of the SARS-CoV-2 virus. The sample will be sent to the study's central lab for analysis by reverse transcription polymerase chain reaction (RT-PCR) with results reported as either 'Detected' or 'Not detected' for SARS-CoV-2 viral particles. If central laboratory testing cannot be performed at the time of Baseline Visit 2 (i.e., lab supplies are not yet available) and the study site is able to perform equivalent testing locally, they may choose to do so, as long as the test results are available in the patient's research chart for sponsor review. Patients should not initiate ATI-450 in the absence of central laboratory or locally equivalent testing being performed.

Patients are allowed to dose with ATI-450 in the interval between sample collection at Baseline Visit 2 and result reporting as long as there is no clinical suspicion of COVID-19 infection or recent exposure of the patient to an individual with a confirmed, active infection.

If the patient's results are positive for SARS-CoV-2 following sample collection at Visit 2, the patient will need to be notified immediately upon receipt of the results and treatment with ATI-450 will be permanently discontinued. The patient should be advised to begin self-isolation and self-monitoring procedures according to any applicable local, state, and/or federal health recommendations. Referral to an appropriate health care provider for management of the patient's COVID-19 diagnosis should also be made. The patient should be seen for the safety follow-up Visit 7 (see Table 1) only at such time that the investigator assesses the risk for incidental transmission from viral shedding to be minimized. The patient's COVID-19 diagnosis will be reported as medical history unless the patient's clinical course progresses such that criterion for SAE reporting is met (See Section 7.1.2), in which case, all applicable safety reporting procedures will be followed by the site.

Sites will also have the option to perform an unscheduled test for the SARS-CoV-2 virus at any time during the treatment phase of the study should a patient's clinical presentation necessitate it in the investigator's opinion. The same notification and referral procedures, as outlined in the preceding paragraphs, should be followed by the site. However, it is expected that any COVID-19 diagnosis made from a sample collected after the initiation of study be reported as an Adverse Event per the requirements of Section 7 of this protocol.

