2 STUDY OBJECTIVES AND ENDPOINTS

The objectives and endpoints for this study are provided in Table 2 below.

Table 2 Study Objectives and Endpoints

Objectives		Endpoints			
Primary	To assess the safety and tolerability of ATI-450 to maintain remission in patients with CAPS previously managed with anti-IL-1 therapy	Number and percent of adverse events (AEs) and serious adverse events (SAEs); mean change from baseline in laboratory values, vital signs, and electrocardiograms (ECGs).			
Secondary	To assess the efficacy of ATI-450 to maintain remission in patients previously managed with anti-IL-1 therapy	 Proportion of participants in disease remission. Disease remission is defined as having a Physician Global Assessment (PGA) score of absent or minimal and a high sensitivity C-reactive protein (hsCRP) and serum amyloid A (SAA) value within the normal range (≤10 mg/L) or within 30 percent of the baseline value. Proportion of participants in clinical remission. Clinical remission is defined as having a PGA score of absent or minimal. Time to relapse; where relapse is defined as a two-point worsening on the PGA scale. Proportion of participants who experience a re-emergence of disease symptoms after discontinuation of ATI-450. Re-emergence is defined as an increase in daily Key Symptom Score (KSS) ≥3 for at least two consecutive days. KSS is derived from the patient-administered daily health assessment form (DHAF). Proportion of participants with a mean KSS no more than 2 points higher than baseline for at least 6 out of 8 weeks during the treatment period. Change from baseline in PGA. Change from baseline in PGA. 			

		Change from baseline in hsCRP and SAA.
Exploratory	 To assess the Pharmacodynamics (PD) of ATI-450 in patients with CAPS To assess the pharmacokinetics (PK) of ATI-450 in patients with CAPS 	 Change from baseline in serum cytokines IL-1β, IL-1α, IL-6, IL-18 and TNF-α ATI-450 concentrations at trough

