7.3 Documenting and Reporting Adverse Events

Reporting of SAEs will begin when the patient has provided informed consent and will continue up to the end of study visit or 30 days after the last ATI-450administration whichever is later. Reporting of AEs will begin when the patient receives the first dose of ATI-450 and will continue up to the end of study visit or 30 days after the last study drug administration, whichever is later. Any clinical AE that occurs between the time of consent and dosing Day 1 will be recorded as medical history.

Occurrence of AEs may be volunteered spontaneously by the patient; discovered as a result of general, nonleading verbal questioning by the study staff; or determined by physical examination or other safety assessments. All AEs will be monitored and recorded in the CRF throughout the entire study.

For all AEs, the investigator must pursue and obtain adequate information (a description of the event, severity, time of occurrence [including whether the AE onset was before, during, or after the study medication administration if the AE started on a dosing day], duration, and any action [e.g., treatment/follow-up tests]). The outcome of the event should be provided along with the investigator's assessment of the relationship to the study medication. The investigator must also assess whether the event meets the criteria for classification as an SAE.

It is the investigator's responsibility to review all documentation (e.g., hospital notes, laboratory reports, and diagnostic reports) related to an AE. Wherever possible, the investigator's diagnosis, not the individual signs and symptoms, will be documented as the AE.

Investigators are not obligated to actively seek AEs or SAEs after the patient's conclusion of study participation. However, if the investigator learns of any SAE, including death, at any time after a patient has been discharged from the study, and he/she considers the event to be reasonably related to the study medication or study participation, the investigator must promptly notify the sponsor.

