8.3 Sample Size

The sample size for this study was determined based upon feasibility constraints as opposed to a formal power computation. Up to 10 patients are planned to be enrolled.

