8.4.2 Safety Analyses

The Safety population will be used for the analysis of safety data (AEs, exposure to study medication, clinical laboratory, vital signs, and ECG).

AEs will be coded with the MedDRA. TEAEs are defined as AEs with an onset date on or after the date of first administration of study medication and before the date of last administration of study medication + 30 days. TEAEs will be presented by system organ class and preferred term in frequency tables. Patients with multiple AEs will be counted only once within each preferred term and system organ class. Key patient information for patients with an AE with an outcome of death, patients with SAEs, and patients with an AE leading to discontinuation of study medication will be listed.

Laboratory data (hematology, serum chemistry, coagulation, lipids, and urinalysis) will be converted to Système International units for reporting and processing purposes. Absolute values and changes from baseline will be presented descriptively. Laboratory data outside study-specific reference ranges will be listed.

Vital signs and ECG parameters will be presented descriptively.

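### Section 5.1.5 files COVID-19 after a positive Day 1 swab as medical history whatever the symptom onset, so non-serious illness starting after the first dose can be left out of the TEAE results

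*Combined protocol and SAP*

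**What the plan says.** Section 5.1.5 requires a swab at Visit 2 before the first dose, but does not require the result first: "Patients are allowed to dose with ATI-450 in the interval between sample collection at Baseline Visit 2 and result reporting", provided COVID-19 is not suspected and there has been no recent contact with a confirmed active case. A positive result ends treatment permanently. The recording rule is then: "The patient's COVID-19 diagnosis will be reported as medical history unless the patient's clinical course progresses such that criterion for SAE reporting is met". Illness that does meet an SAE criterion goes through the usual safety reporting. For unscheduled tests during treatment the same section expects that "any COVID-19 diagnosis made from a sample collected after the initiation of study be reported as an Adverse Event".

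The general rules are these:

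- Section 7.3: "Reporting of AEs will begin when the patient receives the first dose of ATI-450". Medical history is for clinical events between consent and Day 1 dosing. Section 5.1.1 and footnote 5 of Table 1 draw the line at the same place. Section 7.3 also prefers a diagnosis to individual symptoms as the AE entry.
- Section 8.4.2: TEAEs are "AEs with an onset date on or after the date of first administration of study medication", up to 30 days after the last dose. Patients with an AE that led to discontinuation are listed.
- Section 5.3.6: new or worsening abnormalities are reported as AEs, as appropriate.
- Section 7.1.3: a laboratory abnormality that leads to discontinuation has to be recorded as an AE or SAE.

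The number and percent of AEs and SAEs is part of the primary endpoint (Section 2). Section 8.3 sets the size: "Up to 10 patients are planned to be enrolled".

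**The concern.** The sentence in 5.1.5 foresees that the illness may progress after dosing, but sends only serious progression to safety reporting. A non-serious course stays in medical history on a literal reading, even if the first symptom appears after several doses. Dosing before the result is allowed only when nothing points to COVID-19, so in these patients symptoms would normally be recognised after the first dose, which is the period the TEAE definition is meant to cover.

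Non-serious is not the same as trivial. Section 7.2.1 separates severe from serious, so an illness that prevents everyday activities without meeting an SAE criterion would still fall under the medical history rule.

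At stake is the primary safety summary. A dosed patient stays in the denominator while the event may be missing from the numerator. The mandatory stop may also be missing from the AE-based discontinuation listing, because that listing needs an AE record.

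**Working it through.** The plan has no formula or figure to reproduce here. Sample size was "determined based upon feasibility constraints as opposed to a formal power computation", and the analysis is descriptive. The check is one of consistency, followed by simple arithmetic for scale.

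**Step 1: one illness, two records.** Take two patients dosed on Day 1. Each first has non-serious COVID-19 symptoms on Day 3 (an illustrative day) and is then taken off ATI-450.

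- Patient A: the Day 1 swab comes back positive. Under 5.1.5 the diagnosis is medical history. Read literally, there is no AE, no TEAE and no entry in the listing of AEs leading to discontinuation.
- Patient B: the Day 1 swab is negative and an unscheduled Day 3 swab is positive. Under 5.1.5 this is an AE. It meets the 8.4.2 definition and enters both outputs.

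Symptom onset relative to first dose is identical. Only the swab date differs, and 8.4.2 classifies by onset date, not swab date.

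**Step 2: which rules point to capture for Patient A.** Section 7.3 points to an AE, because symptoms on Day 3 fall after its cut-off for medical history. So does 8.4.2, if onset is read as symptom onset. Section 5.3.6 points the same way for abnormalities found on examination. Section 7.1.3 arguably does too, if a PCR result that stops treatment counts as a laboratory abnormality. Only 5.1.5 points the other way. The 7.3 preference for a diagnosis makes separate symptom entries less likely, but does not forbid them.

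**Step 3: denominator.** The synopsis analyses safety in the ITT population, defined in 8.2 as all patients given at least one dose. Section 8.4.2 names a Safety population that 8.2 does not define. I assume it also means all dosed patients, so Patient A counts in N.

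**Step 4: size of one omitted case = 1/N.**

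- N=10: 0/10 = 0% instead of 1/10 = 10%, a step of 10 points.
- N=8: 1/8 = 12.5 points. N=5: 1/5 = 20 points.
- Section 4.4.1 allows replacement of patients who stop early. If that led to 11 dosed patients, the step would be 1/11 = 9.1 points.

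For scale only, exact (Clopper-Pearson) 95% intervals at N=10:

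- 0/10: upper limit 1 − 0.025^(1/10) = 30.8%, so 0 to 30.8%.
- 1/10: lower limit 1 − 0.975^(1/10) = 0.3%; upper limit, the 97.5% point of Beta(2, 9), = 44.5%.

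**Step 5: how likely is any positive Day 1 swab?** The documents give no prevalence, so p below is assumed. The chance of at least one positive in 10 is 1 − (1 − p)^10:

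- p = 0.5%: 4.9%
- p = 1%: 9.6%
- p = 2%: 18.3%
- p = 5%: 40.1%

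These are upper limits for the problem case, which also needs dosing before the result and non-serious symptoms that begin or worsen after dosing.

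**The case against.** The rule has a logic. The swab precedes the first dose, so a positive result shows infection that was present before exposure. Treating that as history is defensible, and calling a pre-existing infection treatment-emergent could overstate the drug's AE rate. Section 8.4.2 does not say whether onset means first symptom or infection. This stands for the swab result itself and for a patient who stays well. It does not settle symptoms that begin or worsen on drug, which 5.1.5 treats in the same way.

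A reader might infer more than the text supports:

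- *That this illness can never reach the AE data.* It can. SAE-level cases are reported. The carve-out names the diagnosis only, and no sentence exempts post-dose symptoms from Section 7. Sites could record them, and 7.1.3 may require an AE. The outcome is ambiguous, not certain exclusion.
- *That the discontinuation disappears.* It does not. Section 6.8 records stop dates, and 4.4.1 lists confirmed SARS-CoV-2 infection as a reason to stop. What may lose the case is the AE-based listing.
- *That a risk named for the drug is removed from view.* Section 1.3 names serious infections, and a case meeting SAE criteria is what the exception in 5.1.5 keeps.
- *That such patients should leave the efficacy ITT set because exclusion criterion 17 makes them ineligible.* Section 8.2 defines ITT as all dosed patients. Changing that is a separate, debatable trade-off and is not needed to repair the AE record.

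The event may also never occur, and no test or decision rule depends on it. That limits the size of the point. It does not make the sections agree.

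**Conclusion.** The point holds as an inconsistency in how AEs are recorded. For non-serious COVID-19 after a positive pre-dose swab, 5.1.5 applies medical history without regard to symptom onset, against 7.3, the onset-based definition in 8.4.2, 5.3.6 and, arguably, 7.1.3. Such illness can therefore be missing from the TEAE tables and the AE-based discontinuation listing, and whether it is may depend on how a site reads the text. Omitting a post-dose event of this kind can only lower the AE count.

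The effect is 1/N per case, or 10 percentage points at N=10, and zero if no case arises. This assumes that onset means symptom onset or worsening and that all dosed patients form the safety denominator. The documents do not support a claim that the primary result is certain to be biased. The correction is worth making because it repairs a stated rule at little cost.

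**What to change.** Reconcile 5.1.5 with 7.1.3, 7.3 and 8.4.2:

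1. In 5.1.5, keep a positive pre-dose swab in a patient without symptoms as medical history.
2. In 5.1.5, state that COVID-19 signs or symptoms with onset or worsening after the first dose are recorded as AEs under Section 7, serious or not, and are classified as TEAEs by the 8.4.2 onset rule.
3. In 8.4.2, tabulate withdrawals for a positive Day 1 swab with that reason, so that they are visible whether or not an AE was recorded.
4. In 7.1.3, say whether a positive PCR result that stops treatment counts as a laboratory abnormality under that section.

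The ITT definition stays as it is. The cost is a few sentences and a routine AE form for any affected patient. The reported AE rate may be slightly less favourable.

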5.2 Efficacy Assessments

5.2.1 Physician Completed Efficacy Questionnaire

The Physician's Global Assessment of Autoinflammatory Disease Activity (PGA) is a measure to be completed by the investigator or designee. The PGA uses a 5-point rating scale: absent, minimal, mild, moderate, and severe. The investigator will select a rating based on the patient's current disease activity at the time of the visit.

5.2.1.1 Maintenance of Disease Remission and Clinical Remission

Maintenance of disease remission will be assessed during the treatment period. Disease remission is defined as having a PGA score of absent or minimal and a hsCRP and SAA value within the normal range (≤10 mg/L) or within 30 percent of the baseline value.

Maintenance of clinical remission will be assessed during the treatment period. Clinical remission is defined as having a PGA score of absent or minimal.

